7.5. Safety Monitoring

A DSMB for METRICAL will act in an advisory capacity to the National Institute on Aging (NIA) Director to monitor participant safety, data quality, and progress of the study. External DSMB members will be specified by the funding agency. Members of the METRICAL team who will participate in the open sessions of the DSMB include the PI ([name]), the lead biostatistician ([name]), and project director ([name]). The NIA project officer for METRICAL, [name], will attend DSMB meetings and serve as the liaison between the DSMB and NIA.

8 INTERVENTION DISCONTINUATION

The study may be discontinued at any time by the IRB, the NIA, the OHRP, or other government agencies as part of their duties to ensure that research participants are protected. Individual facilities in the intervention may withdraw from study participation at any time at the discretion of their senior management or corporate supervisors. Individual residents or their proxies can refuse the intervention and/or the observation of the implementation of the intervention.

9 STATISTICAL CONSIDERATIONS

9.1 General Design Issues

We will conduct two parallel, cluster-randomized control trials (RCTs) of personalized music for nursing home (NH) residents with moderate to severe dementia cared for in 81 NHs within four NH health care systems: PruittHealth, Good Samaritan Society, Vetter Senior Living, and CommuniCare (Terrapins Division). Twenty-seven facilities will receive the intervention in each trial.

9.2 Sample Size and Randomization

The primary outcome for this study is agitated and aggressive behaviors, as measured by the Cohen-Mansfield Agitation Inventory (CMAI). We have three ways of measuring agitation and aggression – the Minimum Data Set (MDS), the Cohen-Mansfield Agitation Inventory (CMAI), and the direct observation of residents while using and not using the music. Prior research suggests that agitated behaviors are underascertained in the MDS, due to staff normalizing these behaviors when exhibited by the residents.(86) For this reason, we chose the CMAI as our primary study outcome. We based our sample size estimates and analytic plan on the CMAI (staff interview).

Sample size estimates are based on the primary trial outcome: total score on the CMAI among long-stay residents with dementia. Based on data from the first trial, We conducted a *post hoc* power calculation to estimate the required sample size for different effect sizes. We used the formula proposed by Teerenstra et al (2012) and imputed values from the trial data. For significance level α and power 1- β , the formula for the required number of residents is:

$$n_{res} = \frac{2\left(Z_{1-\frac{\alpha}{2}} + Z_{1-\beta}\right)^2 \sigma^2}{\delta^2} (1 + (n-1)\rho)(1-r^2),$$

where Z_x is the critical value from a normal distribution at x, σ^2 is the variance of the outcome CMAI, δ is the effect size, ρ is the intra-class correlation, n is the number of residents per cluster and r is the correlation between a cluster means at baseline and at follow-up. To obtain the number of clusters required per arm we would need n_{res}/n . In our parallel design experiment completed just before the pandemic, we found that $\sigma = 20$, $\rho = 0.12$ and r = 0.5. Assuming an alpha level of 0.05 and power of 80%, we need 24 NHs per study arm to detect a 6-point reduction in the total CMAI score. We recruited 27 NHs per study arm which will allow us to address possibly higher ICC values, non-participation and lower correlation between the baseline and outcome scores.

9.2.2. Treatment Assignment Procedures: Please refer to section 4 for a detailed description of the treatment assignment procedures.

9.2.3. Blinding: Our partner health care systems will know which facilities are designated intervention facilities. Brown University statistician and data management staff will present aggregated post-random assignment comparisons of intervention and control facilities' baseline characteristics, but these preliminary analyses will be not generated at the individual facility level. [name], the study PI, will be blinded to the identity of both the control and intervention facilities. Facility assignment will be unblinded to the DSMB members at their request.

9.3 Interim analyses and Stopping Rules

We do not include stopping rules in the METRICAL trial protocol for two reasons. First, this is a minimal risk study for which serious negative reactions will be extremely rare (see Section 7.1). Indeed, the Brown IRB has concurred with this interpretation, having allowed a waiver of consent specifically because they view the study as minimal risk. Second, a stopping rule would not be very feasible since the implementation period is only 8 months in each facility, meaning that interim data analyses will be difficult, if not impossible, to perform.

9.4 Outcomes

9.4.1 Primary outcome

The primary outcome for this study is the frequency of agitated and aggressive behaviors, as measured by the CMAI. The CMAI has 29 items organized under three domains: aggressive behavior, physically nonaggressive behavior, and verbally agitated behavior.(83) For each item, a staff member familiar with the resident's behavior is asked how often each behavior occurred in the past week. Response choices are: never (1); less than once a week (2); once or twice a week (3); several times a week (4); once or twice a day (5) several times a day (6); or several times an hour (7). For NH residents with dementia the inter-observer reliability of the CMAI was: .62 for physically aggressive behaviors (reliable change index, RCI = 7.54), .73 for physically non-aggressive behaviors (RCI = 7.09), and .61 for verbally agitated behaviors (RCI = 5.80).(87)

Test-retest reliability was: .82 for physically aggressive behaviors (reliable change index, RCI = 2.59), .83 for physically non-aggressive behaviors (RCI = 5.44), and .86 for verbally agitated behaviors (RCI = 3.22).(87) During the R21 phase, the average total CMAI score for eligible residents at baseline was 60.98 (SD:15.37). Average total CMAI scores were similar across nursing home corporations (Table 3).

	Obs	Mean	SD	Min	Max	Kurtosis
Overall	42	60.98	15.37	30	95	2.41
Good Sam	10	63.90	20.23	38	95	1.65
Vetter	12	59.58	13.79	38	89	3.10
Pruitt	10	58.20	10.35	42	77	2.39
CommuniCare	10	62.50	17.44	30	86	2.44

9.4.2. Secondary Outcomes:

Secondary outcomes are obtained from primary and secondary data sources.

Primary Data

Agitated and aggressive behaviors. The Agitated Behaviors Mapping Instrument (ABMI). The ABMI has 14 items which can be collapsed into total agitation, verbal agitation, and physical agitation.(90) Interrater reliability (IRR) for identification of behavior exceeds 90% in Cohen-Mansfield's publications (93%, 96%); reported intraclass correlations coefficient (ICC) .90.(90-92) Cohen-Mansfield also reports high ICCs between videotaped (blinded) coding of behaviors and direct observation of behaviors (not blinded): .94 for verbal agitation, .93 for physical nonaggressive agitation, and .94 for total agitation.(90) Pearson correlation coefficients for identical items on the ABMI and CMAI are: .317 for verbal agitation (requests for attention .372, screaming .432, cursing .168, and complaining .442); .389 for physical agitation (pacing .542, repetitions .555, and exit seeking .322); .203 for combined agitation; .411 for physical aggression and .400 for disruptiveness.(93)

Mood. Mood states are also observed using the Lawton Observed Emotion Rating Scale (OERS),(85) which was designed to measure pleasure, anger, anxiety/fear, sadness, and general alertness in nursing home residents with ADRD.

Secondary Data

Agitated and aggressive behaviors. In addition to the CMAI and the ABMI, we will also measure agitation and aggressive behavior using the MDS. The Aggressive Behavior Score (ABS) is derived from four items in MDS, Section E, which describe the frequency of: 1) physical behaviors (hitting kicking, pushing, etc.); 2) verbal behaviors (threatening, screaming, cursing, etc.); 3) other behaviors (scratching self, pacing, throwing, smearing food, etc.); and 4) rejection of care. Each behavior problem is rated in its frequency, ranging from 0 (never) to 3 (daily), and the ABS is constructed by summing these four items. It has an alpha reliability between 0.79 and 0.93.(95)

Receipt of antipsychotic medications and their substitutes. We have two data sources for receipt of antipsychotic, antidepressant, and anxiolytic medications: electronic medication orders and the MDS. The MDS assessment includes a count of the number of days in the last 7 in which an antipsychotic, antidepressant, and anxiolytic medication was received. We are also receiving standing medication orders from all four corporations. This data includes drug name and class, order date, ordering physician, and number of pills.

Mood. The MDS includes the Patient Health Questionnaire (PHQ-9) a validated measure of depressed mood asked of the residents or if unable to respond to the interview, rated by staff.(96)

9.4.3. Process Measures for Implementation Analysis:

We will adopt five distinct approaches to assessing implementation: 1) a user-defined assessment (UDA) by which potentially eligible residents are assessed for their ability to listen to music, their music preferences, and the results of the initial trial of the iPod; 2) iPod metadata about each song that is played, including a count of the times played (and therefore the sum of all plays per unit time); 3) documentation of NH staff participation and attendance in M&M training and monthly corporation calls; 4) key informant interviews of NH staff during and after implementation; and 5) implementation observation checklist, completed on-site by data collectors, to

describe adherence to specific aspects of the study protocol (e.g., are the playlists individualized, are the iPods labeled, etc). Table 4 describes the relationship between primary and secondary data sources and study outcomes.

Me 4. Relationship of Data Sources to S	luuy Oulcom	63				
	Agitation / Aggression	Mood	Antipsychotic Mediation	Anxiolytic Medications	Antidepressant Medications	Implementation
Secondary Data						
Minimum Data Set	X	Х	Х	Х	Х	
User Defined Assessment						Х
Medication Order Records			Х	Х	Х	
Primary data						
Staff Interview	X					
Resident Observation	X	Х				
iPod Metadata						Х
Key Informant Interview						Х
Implementation observation						Х

Table 4 Deletionabi	n of Doto Sourc	an to Stud	/ Outcomes
Table 4. Relationshi	p of Data Sourc	es lo siud	Vulcomes

9.5 Data Analyses

The analytic approach in the second parallel trial is based on the minimum observed frequency of agitated and aggressive behaviors after intended exposure to the intervention (treatment) or after 8-months (control), conditional upon survival to at least one post-intervention observation (up to 4 months after baseline measurement). Our primary analysis is based upon an intent-to-treat principle, and we estimate complier average causal effect as a secondary analysis. The compliers analysis estimates the effects of the intervention for residents who received the music or would have received the music.

Our primary ITT analysis model is based on the model described by Murray & Blistein (2003) and Teerenstra et al (2012). Let Y_{ijk} be the staff interview for resident $i \in \{1, ..., n\}$ from NH $j \in \{1, ..., J\}$ at time $k \in \{baseline, post - exposure\}$, I_{ij} be an indicator that is equal to 1 if resident i in facility j is in the treatment group and T_{ij} is an indicator that is equal to 1 if this is the baseline score for resident i in facility j. We assume that $Y_{ijk} = \mu_{ijk} + \epsilon_{ijk}$, where $\epsilon_{ijk} \sim N(0, \sigma_{\epsilon}^2)$, and $\mu_{ijk} = \mu + \gamma T_{ij}I_{ij} + \tau(1 - T_{ij})(1 - I_{ij}) + \alpha(1 - T_{ij})I_{ij} + u_j + (u\tau)_{j,k} + s_{ij}$. We define $u_j \sim N(0, \sigma_u^2)$ as the deviation of cluster j from the overall mean, $(u\tau)_{j,k} \sim N(0, \sigma_{u\tau}^2)$ represent the variation of each cluster at different time points, $s_{ij} \sim N(0, \sigma_s^2)$ is the variation of individuals, γ is the difference at baseline between the mean of the intervention and control clusters, τ is the change from baseline to follow-up of the control clusters means, and α is the conditional treatment effect. Individual level covariates comprise of baseline variables including baseline CMAI. The estimate of interest would be the difference in marginal means.

To estimate the effects among participants that would comply with the intervention we used a technique described by Jo et al. Let c_{ij} be an indicator that is equal to 1 if resident *i* in NH *j* would use the music if provided. We assume that residents who would not be offered the music will not attempt to obtain it on their own. Eligible residents who do not receive the intervention who and receive care in an intervention NH are referred to as "non-compliers." The effects of the intervention would be estimated using, $\mu_{ij} = \beta_0 + \beta_c c_{ij} + \alpha_c c_{ij} I_{ij} + \sum_{l=1}^{L} \gamma_{ijl} X_{ijl} + u_{nbj}(1 - c_{ij}) + u_{nwij}(1 - c_{ij}) + u_{cwij}c_{ij} + u_{cbj}c_{ij}$, where the macro-unit residuals u_{nbj} (non-compliers) and u_{cbj} (compliers) represent cluster-specific effects given I_{ijk} and X_{ijl} , which are assumed to be normally distributed with zero mean and the between-cluster variances σ^2_{nb} (non-compliers) are assumed to be normally distributed with zero mean and the within-cluster variance σ^2_{nw} (non-compliers) are assumed to be normally distributed with zero mean and the within-cluster variance σ^2_{nw} (non-compliers) are assumed to be normally distributed with zero mean and the within-cluster variance σ^2_{nw} (non-compliers) are assumed to be normally distributed with zero mean and the within-cluster variance σ^2_{nw} (non-compliers) are assumed to be normally distributed with zero mean and the within-cluster variance σ^2_{nw} (non-compliers) are assumed to be normally distributed with zero mean and the within-cluster variance σ^2_{nw} (non-compliers) are assumed to be normally distributed with zero mean and the within-cluster variance σ^2_{nw} (non-compliers) and σ^2_{cw} (compliers), and are equal across clusters. The following model for compliance status was assumed:

$$P(C_{ij} = 1) = \frac{exp\left(\sum_{l=1}^{L} \pi_{ijl}X_{ijl} + \tau_j\right)}{1 + exp\left(\sum_{l=1}^{L} \pi_{ijl}X_{ijl} + \tau_j\right)}$$

Where π_{ijl} are unknown parameters and $\tau_j \sim N(0, \sigma_\tau^2)$ so that the proportion of compliers may vary across clusters. Compliance status is only known in the intervention arm. Thus, a mixture model for compliance status in the control arm would be applied. Using the full likelihood, parameter estimates of the effect among compliers are estimated

$$\hat{\delta} = \left(\hat{\delta}_1 - \hat{\delta}_0\right) / \rho_c$$

where $\hat{\delta}_t$ are the average CMAI among compliers in treatment group t and where ρ_c is the proportion of compliers. $\hat{\delta}_t$ can be obtained from the above models across NHs. The variance of this estimate can be obtained via the delta method or using Markov chain Monte Carlo techniques.

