Aim 2 of this study is to estimate the impact of M&M on agitated and aggressive behaviors in NH residents with moderate to severe dementia. Agitated and/or aggressive behaviors are measured three ways: by interviewing staff about resident behaviors over time (primary outcome); through direct observation of residents when using and not using M&M (secondary outcome); and using available administrative data (secondary outcome). Other secondary outcomes include: other emotional states directly observed while the resident is using and not using M&M (anger, pleasure, alertness, sadness), antipsychotic use, antidepressant use, anxiolytic use, and depression. In this cluster RCT, the unit of random assignment is the facility, but the unit of analysis is the patient, clustered within the facility. The analytic approach we propose is based upon the cumulative likelihood of reductions in agitated and aggressive behaviors in a long-stay population with moderate to severe dementia, conditional upon survival to at least one post-intervention observation. Outcomes will be evaluated using a repeat parallel design, comparing wave 1 (intervention) and wave 2 (control) NHs (n=54) in the first study year, and wave 2 (intervention) and wave 3 (control) NHs (n=54) in the second study year. The repeat design allows for modification of the intervention delivery between waves to increase adherence. Since we do not expect the intervention to affect mortality, the comparison will be based on the last observed total agitation score among residents meeting eligibility criteria in the treated and control groups. All deaths among exposed and control populations will be routinely controlled and reported to the data safety and monitoring board for monitoring purposes. Facilities will be stratified by corporation, and balanced on baseline agitated and aggressive behaviors and number of eligible residents, prior randomization. Because we are interested in the effect of the intervention among those who use it, we will also conduct an as-treated analysis, using a technique described by multilevel-mixture analysis for analyzing cluster randomized data with non-compliance.

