5 STUDY INTERVENTIONS

5.1 Interventions, Administration, and Duration

The M&M personalized music program will be implemented for at least 8 months in each intervention facility. (Obviously, facilities are encouraged to continue to use the music devices with patients long after this 8-month period and the devices will remain at the facility for use among appropriate patients). The intervention consists of: 1) identifying the music a resident with ADRD preferred when she was between the ages of 18 and 24, either by consulting family members or through trial and error; 2) creating a personalized playlist for each resident; 3) loading this personalized playlist on the resident's music player (iPod); and 4) using the iPod with the resident twice a day for approximately 30 minutes to 1 hour per use, at times when residents with ADRD tend to experience BPSD. Recommended times are when the resident gets up in the morning (during daily personal care) and in the late afternoon, when sundowning is common. In addition to these set times, NH staff are encouraged to use the music at other times when an individual resident is likely to experience BPSDs. In the first parallel trial. NH staff will be responsible for completing all four steps. In the second parallel trial. research staff will create personalized playlists (step 2) and load music players (step 3). For the second parallel trial, staff will provide Brown with 15 eligible residents' "preferred" music genre and resident age. Brown research staff will preload iPods with popular music in the resident's preferred genre from when they were between the ages of 16 and 26 (current best practice recommendation). This process is similar to playlists generated by Spotify and other streaming services. Additionally, we will be using playlists from the first trial to culturally and regionally tailor music selections. This is particularly important for the current study as we have four regionally and racially diverse corporations: two NH corporations serving predominately white, rural

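### Section 9.5 takes the second trial's primary CMAI score as a minimum, the Précis takes the last observed value, and 9.5 does not name the visits that feed it

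*Combined protocol and SAP*

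**What the plan says.** Section 9.5 opens with the rule for the second trial: "The analytic approach in the second parallel trial is based on the minimum observed frequency". The timing is worded separately by arm: "minimum observed frequency of agitated and aggressive behaviors after intended exposure to the intervention (treatment) or after 8-months (control"). Inclusion is "conditional upon survival to at least one post-intervention observation (up to 4 months after baseline measurement"). The intent-to-treat model then has two time levels, "baseline, post - exposure", and does not say which visit the second one is.

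The Précis (Design and Outcomes, Aim 2) gives another rule: "the comparison will be based on the last observed total agitation score among residents meeting eligibility criteria in the treated and control groups". The same paragraph describes both comparisons, including "wave 2 (intervention) and wave 3 (control) NHs (n=54) in the second study year", so it cannot be set aside as text about the first trial. It also calls the approach "based upon the cumulative likelihood of reductions in agitated and aggressive behaviors".

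On visits, section 6.1 lists baseline, 4 and 8 months for primary data. It marks resident observation as Trial 1 only, but not the CMAI staff interview. The Table 1 footnote places primary data collection in Sequences 2 and 3 in Period 3. The detailed visit procedures in section 10.1 are, however, headed as applying to Trial 1 only. Sections 9.2 and 9.4.1 name the CMAI as the outcome without a visit or a summary rule.

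**The concern.** A resident with scores at months 4 and 8 has one value under the minimum rule and possibly another under the last-observed rule. The plan therefore allows two primary scores for the second trial, and an analyst could follow either and cite the protocol. The choice would then be made after the plan was written, possibly with data in hand.

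This matters even if neither rule is biased. The minimum rewards an improvement at either visit. The last observed score reflects the state at the end of follow-up. The two agree when the effect is the same at both visits and diverge when it builds up or fades between them. The sample size in 9.2 is for a difference in mean score at one follow-up and does not settle the matter.

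**Working it through.** **Inputs.** From 9.2: SD σ = 20, ICC 0.12, baseline correlation r = 0.5, target 6 points, α = 0.05, power 80%, 27 homes recruited per arm. The Précis makes the test two-sided. From Table 1: 405 residents in 27 homes, so 15 per home. Assumed: both follow-up scores exist, are normal and have equal SD, with correlation w from 0.5 to 0.9. The documents do not give w. The subscale test-retest values of .82 to .86 in 9.4.1 are only a loose guide, because they are not for the total score and no interval is stated.

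**1. The plan's own figure.** Residents per arm = 2 × 7.849 × 400/36 × (1 + 14 × 0.12) × (1 − 0.25) = 350.6. Divided by 15 this is 23.37, rounded up to 24. The plan's 24 homes per arm is reproduced for a single follow-up score.

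**2. Same rule in both arms, 6 points at month 8 only, all residents seen twice.** Last observed gives 6.0. For the minimum, let θ = σ√(2(1 − w)) and d = 6. The effect is d·Φ(d/θ) + θ·[φ(d/θ) − φ(0)].
- w = 0.5: θ = 20, and 6 × 0.6179 + 20 × (0.3814 − 0.3989) = 3.36.
- w = 0.9: θ = 8.944, and 6 × 0.7488 + 8.944 × (0.3186 − 0.3989) = 3.77.
- At w = 0.7, 0.8 and 0.86 the results are 3.46, 3.56 and 3.66.

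**3. Same rule, 6 points at month 4 only.** Last observed gives 0. By symmetry the minimum gives the same 3.4 to 3.8.

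**4. Same rule, 6 points at both visits.** Both rules give 6.0.

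**5. What step 2 means for power.** With the plan's variance formula and 27 × 15 residents, SE = √(2 × 400 × 2.68 × 0.75/405) = 1.99. Power for 6.0 points is Φ(6/1.99 − 1.96), about 85%. For the minimum I use its SD under no effect, σ√(1 − (1 − w)/π), which is 18.34 to 19.68, so SE is 1.83 to 1.96. I keep r = 0.5. Power for 3.4 to 3.8 points is then about 45% to 49%.

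**6. Unequal completeness under a minimum.** A minimum over two scores lies σ√((1 − w)/π) below a single score: 7.98 points at w = 0.5 and 3.57 at w = 0.9. If the arms differ by 10 percentage points in residents with both scores, a minimum rule shifts under no effect by a tenth of that, about 0.8 to 0.4 points.

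**The case against.** The strongest reply is that a trial-specific analysis section should outrank a summary, so 9.5 governs. That is a reasonable convention, but the protocol does not state it, the Précis expressly covers the second trial, and 9.5 still does not name the visits. A second reply is that the two rules coincide if there is only one follow-up CMAI. That is true, and the heading of 10.1 leaves it possible, but 6.1 points to two.

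Four stronger readings are tempting and should not be adopted.
- **A built-in bias.** A reader might infer that treated residents contribute the lower of two scores and controls only month 8. Taken literally, and ignoring deaths, that would create a spurious benefit of 3.6 to 8.0 points (step 6) against a 6-point target. The documents do not support this as the intended meaning. The programme "will be implemented for at least 8 months in each intervention facility" (section 5.1), so the two timing phrases most naturally describe the same window. The at-least-one-observation condition is not arm-specific: under this reading a control who reached month 4 but not month 8 would qualify and have no score. It is the least coherent reading.
- **No visits stated.** Section 6.1 does give a schedule. The gap is which of those visits enter the trial 2 score.
- **Three rival scores.** The phrase about cumulative likelihood is not used in the sample size or the model. It needs aligning, but it is not a working definition.
- **A conflict with the model.** A single post-exposure value is compatible with either a minimum or a last observed score.

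**Conclusion.** The plan is wrong as written. Section 9.5 and the Précis give different summary rules for the second trial's primary score, and nothing in the protocol reconciles them. If both follow-up scores exist, the difference is material: 6.0 against 3.4 to 3.8 points when a 6-point effect is present only at month 8, and 0 against 3.4 to 3.8 when it is present only at month 4. The rules agree when the effect is constant. These figures assume normal scores, SD 20, w between 0.5 and 0.9, and no deaths.

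The conflict between the rules is certain from the text. Its size depends on w, on how the effect changes over time, and on there being two follow-up CMAIs. No bias in favour of the intervention is shown: it would arise only under an arm-specific reading that the rest of the plan argues against. The figure of 24 homes per arm is not in error.

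**What to change.** In 9.5, replace the minimum and the arm-specific timing with one rule for both arms: the last observed post-baseline CMAI total score (month 8, else month 4), with the same at-least-one-observation condition. Name the trial 2 visits that feed it. This agrees with the Précis and fits the single post-exposure time in the model.

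If the minimum is kept, take it over the same visits in both arms, change the Précis to match, and state that it shifts under no effect when the arms differ in how many residents have both scores (about 0.4 to 0.8 points per 10 percentage points).

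In either case, align the cumulative-likelihood wording in the Précis with the chosen rule, and make 6.1 and the heading of 10.1 consistent on CMAI visits in trial 2. The cost is wording only, provided that the month 4 and month 8 CMAIs are collected in trial 2 as 6.1 indicates.

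### Section 9.5 primary model: α as printed is not the treatment effect, the tested contrast is given only in words, and baseline CMAI appears twice; fitted as printed with γ free, the model lacks the precision assumed in Section 9.2

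*Combined protocol and SAP*

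**What the plan says.** Section 9.5 models the staff-interview score in two rows per resident, baseline and post-exposure. I marks the intervention arm, and T "is an indicator that is equal to 1 if this is the baseline score". The fixed part of the mean is μ + γ·T·I + τ·(1 − T)(1 − I) + α·(1 − T)·I, with random effects for home, home by time, and resident.

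The parameters are described in words. For the control arm, "τ is the change from baseline to follow-up of the control clusters means". The symbol γ stands for the gap between the arms before the intervention starts. On the effect of interest and the adjustment variables, the section says: "α is the conditional treatment effect. Individual level covariates comprise of baseline variables including baseline CMAI". The equation contains no covariate term. The target is given in one sentence: "The estimate of interest would be the difference in marginal means".

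Section 9.2 sizes the trial with a formula that includes the factor (1 − r²), where "r is the correlation between a cluster means at baseline and at follow-up". With σ = 20, ρ = 0.12 and r = 0.5 it concludes that "we need 24 NHs per study arm to detect a 6-point reduction in the total CMAI score", at 80% power and α = 0.05 (two-tailed, according to the Précis). The 27 homes per arm recruited are presented as a reserve against stronger clustering, loss of homes and a weaker baseline correlation.

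**The concern.** A programmer given Section 9.5 would have to make three choices that the text leaves open: which combination of γ, τ and α to test, whether and where baseline CMAI enters as a covariate, and whether γ is estimated. The label on α points to a quantity that mixes the treatment effect with the control-arm change. The double use of baseline CMAI is harmless in one placement and damages the standard error in another.

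This is the primary test. If these choices remain open until outcomes are visible, the analysis is not fully pre-specified. In addition, the precision claimed in Section 9.2 belongs to a baseline-adjusted comparison, and the model printed in Section 9.5 does not deliver it when γ is free.

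**Working it through.** **1. Cell means of the printed model (T = 1 at baseline)**

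| | Baseline | Follow-up |
|---|---|---|
| Control | μ | μ + τ |
| Intervention | μ + γ | μ + α |

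So α is intervention follow-up minus control baseline. With no treatment effect and no baseline difference, α = τ, not 0. The follow-up difference is α − τ, and the difference in change is α − γ − τ.

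As an illustration with an assumed control change of −3 points: the SE of α at 27 homes is 2.30 (step 3), and 3/2.30 = 1.30. A test of α = 0 would then reject a true null about 26% of the time.

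**2. Reproducing Section 9.2**

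Inputs: σ = 20, ρ = 0.12, r = 0.5, δ = 6, two-sided 5%, 80% power (Section 9.2 and Précis). Section 9.2 gives no value for n; n = 15 is inferred from Table 1 (405/27).

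- Homes per arm = 2(1.96 + 0.84)² × 400/36 × (1 + 14 × 0.12) × (1 − 0.25)/15 = 350.6/15 = 23.4, so 24. The plan's figure is reproduced.
- Without the (1 − r²) factor the result is 31.2, so 32.

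**3. Variance under the printed model with γ free**

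With four free cell means and balanced complete data, α − τ is the plain difference in follow-up means, so its variance factor is 1. The factor for α − γ − τ is 2(1 − r), which is also 1 at r = 0.5.

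SE = √[2 × 400 × 2.68 × f/(15 × homes)], and power = Φ(6/SE − 1.96):

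| Homes per arm | f = 0.75 (Section 9.2) | f = 1 (printed model, γ free) |
|---|---|---|
| 24 | SE 2.11, 81% | SE 2.44, 69% |
| 27 | SE 1.99, 85% | SE 2.30, 74% |
| 32 | – | SE 2.11, 81% |

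Sensitivity of the 74%: n from 10 to 20 gives 68–78%. For α − γ − τ, r = 0.4 gives 66% and r = 0.6 gives 83%.

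**4. Where baseline CMAI goes (simulation)**

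Settings: 27 homes per arm, 15 residents per home, SD 20, ICC 0.12, home-mean r = 0.5, REML. One set used 3,000 runs per setting with resident autocorrelation 0.2–0.8. A second used 1,500 runs with 0.5–0.91. The documents do not give this autocorrelation.

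- *Two rows, γ free, covariate on follow-up rows only* (first set): type I error 5–6% for both contrasts and power 72–75%. The fitted slope averages 0.00–0.02 and the mean SE stays at 2.30. The random effects already carry the link between the two rows, so the covariate adds nothing.
- *Two rows, γ free, covariate in both rows with one slope*: type I error for α − τ is 13–18% in the first set and 16–19% in the second. In the first set the mean model SE is 1.52–1.55 against an actual SD of 2.00–2.23. For α − γ − τ, type I error is about 7–9%.
- *One row, follow-up ANCOVA on resident baseline*: type I error 5–7%. Power is 81–85% in the first set and about 77–86% in the second.
- *The same plus home-mean baseline CMAI* (first set): power 84–85%.
- *Two rows, γ = 0, common τ, no covariate*: type I error 5–7%, power about 85–86%.

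The simulations assume equal home sizes, no deaths, and no corporation or triplet effects.

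**The case against.** The strongest reply is that the intent can be read from the text. A conditional effect, baseline CMAI among the covariates and a (1 − r²) sizing factor all point to a baseline-adjusted follow-up comparison, and Sections 9.2 and 9.5 cite the same published method for sizing and model. That comparison is sound and agrees with the 24 homes. This stands: the fault lies in what is printed, and about 74% power is one branch of the ambiguity. The gap also depends on the unknown resident autocorrelation, since at the low end the ANCOVA gives about 77%, only 3 points above 74%.

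Four stronger readings are tempting but not supported:

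- *That the plan tests α.* No sentence says so. The stated target is a difference in marginal means, and with a post-exposure outcome the natural reading is α − τ.
- *That 24 homes is an error.* It reproduces exactly under its own formula.
- *That the plan promised 85% power.* It states 80% at 24 homes. The 85% is only that formula evaluated at 27 homes.
- *That any two-row model loses precision.* With γ = 0 and a common τ it does not.

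It is also fair that the homes are already recruited, so the 32-home figure cannot change enrolment. It only shows that, with γ free, the reserve of 27 over 24 is already spent.

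**Conclusion.** The point holds as a defect in the written analysis. Three parts follow from the text alone and need no assumptions: α is not the treatment effect unless τ = 0; the contrast is given in words that fit both α − τ and α − γ − τ; and baseline CMAI is used both as an outcome and as a covariate without a place in the equation.

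The numerical consequence is conditional. If the two-row model is fitted with γ estimated and no effective baseline adjustment, power is about 69% at 24 homes against the stated 80% (81% by the formula), and about 74% at 27 homes. This rests on n = 15 and, for the change contrast, on r = 0.5. The inflated type I error of about 13–19% applies to α − τ only when the covariate enters both rows under one slope. Confidence is high for the algebra and moderate for the power figures.

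**What to change.** Write one model, give the tested contrast as a formula, and use baseline CMAI once. Either of these would do:

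1. **One row per resident.** Follow-up CMAI = μ + θ·arm + β·baseline CMAI + other baseline covariates + nursing-home random effect + residual, with θ as the treatment effect. Adding home-mean baseline CMAI is optional; it matches the definition of r on home means in Section 9.2.
2. **Two rows per resident.** Set γ = 0, replace τ(1 − T)(1 − I) by a common τ(1 − T) in both arms, and drop baseline CMAI as a covariate. Then α is the treatment effect.

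If γ is kept free instead, restate the power in Section 9.2 without the (1 − r²) factor.

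The cost is SAP wording only: same data, same homes.

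A separate item, on which none of the figures above depend: the follow-up score needs one definition, the same in both arms. Under Design and Outcomes, the Précis says "the comparison will be based on the last observed total agitation score among residents meeting eligibility criteria in the treated and control groups", while Section 9.5 describes the second trial's approach as "based on the minimum observed frequency of agitated and aggressive behaviors after intended exposure to the intervention". The two should be reconciled, or the difference between trials stated.
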